5.2.1.2 CHANGES IN BLOOD PRESSURE

As a potent loop diuretic compound, [REDACTED] is as an anti-hypertensive drug. Hypotension and dizziness have been reported in approximately 1% of the patients taking [REDACTED] [REDACTED] [REDACTED]. In this study, assessment of BP, including orthostatic BP, will be performed at each study visit. If considered needed, symptomatic treatment should follow standard of care. Additional assessments of vital signs might be considered by the investigator.

5.2.1.3 SUICIDALITY

Clinical data does not point to any suicidality liability of [REDACTED]. However, monitoring for suicidality is mandatory in clinical trials of CNS-active molecules and will be implemented as outlined in [Section 4.6.1.8](#) and [Appendix 1](#). The Investigator is asked to assess individually appropriate next steps in case a suicidality alert arises.

5.3 METHODS AND TIMING FOR CAPTURING AND ASSESSING SAFETY PARAMETERS

The investigator is responsible for ensuring that all AEs (see [Section 5.1.1](#) for definition) are recorded on the AE eCRF page and reported to the sponsor in accordance with instructions provided in this section and in [Sections 5.4](#) through [Section 5.6](#).

For each AE recorded on the AE eCRF page, the investigator will make an assessment of seriousness (see [Section 5.1.2](#) for seriousness criteria), severity (see [Section 5.3.3](#)), and causality (see [Section 5.3.4](#)).

5.3.1 ADVERSE EVENT REPORTING PERIOD

Investigators will seek information on AEs at each patient contact. All AEs, whether reported by the patient or the caregiver or noted by study personnel, will be recorded in the patient's medical record. AEs will then be reported on the AE eCRF page as follows:

After informed consent has been obtained but prior to initiation of study drug(s), only SAEs caused by a protocol-mandated intervention should be reported (e.g., SAE related to invasive procedures such as biopsies).

After initiation of study drug(s), all AEs, regardless of relationship to study drug(s), will be reported until the follow-up visit (i.e., 2 weeks after the last dose of study drug[s]).

At the end of the 2-week follow-up period, investigators should report any deaths, SAEs, or other AEs of concern that are believed to be related to prior treatment with study drug(s) (see [Section 5.6](#)).

5.3.2 ELICITING ADVERSE EVENT INFORMATION

A consistent methodology of non-directive questioning should be adopted for eliciting AE information at all patient evaluation time-points. Examples of non-directive questions include the following:

“How have you felt since your last clinic visit?”

“Have you had any new or changed health problems since you were last here?”

5.3.3 ASSESSMENT OF SEVERITY OF ADVERSE EVENTS

[Table 3](#) provides guidance for assessing AE severity.

Table 3 Adverse Event Severity Grading Scale

Severity	Description
Mild	A type of AE that is usually transient and may require only minimal treatment or therapeutic intervention. Discomfort noticed, but no disruption of normal daily activity.
Moderate	A type of AE that is usually alleviated with specific therapeutic intervention. The event interferes with usual activities of daily living, causing discomfort but poses no significant or permanent risk of harm to the research subject. Discomfort sufficient to reduce or affect normal daily activity.
Severe	A type of AE that interrupts usual activities of daily living, significantly affects clinical status, may require intensive therapeutic intervention, or is incapacitating with inability to work or to perform normal daily activity. The term “severe” does not necessarily equate to “serious”.

Note: Regardless of severity, some events may also meet seriousness criteria. Refer to definition of a serious adverse event (see [Section 5.1.2](#)).

5.3.4 ASSESSMENT OF CAUSALITY OF ADVERSE EVENTS

Investigators should use their knowledge of the patient, the circumstances surrounding the event and an evaluation of any potential alternative causes to determine whether or not an AE is considered to be related to the study drug(s), indicating “yes” or “no” accordingly as per below definitions:

- **Related:** The AE is known to occur with the study intervention, there is a reasonable possibility that the study intervention caused the AE or there is a temporal relationship between the study intervention and event. Reasonable possibility means that there is evidence to suggest a causal relationship between the study intervention and the AE.
- **Not related:** There is not a reasonable possibility that the administration of the study intervention caused the event, there is no temporal relationship between the study intervention and event onset or an alternate etiology has been established.

The following guidance should be taken into consideration:

- Temporal relationship of event onset to the initiation of study drug(s).
- Course of the event, considering especially the effects of dose reduction, discontinuation of study drug(s), or reintroduction of study drug(s) (where applicable).
- Known association of the event with the study drug(s) or with similar treatments.
- Known association of the event with the disease under study.
- Presence of risk factors in the patient or use of concomitant medications known to increase the occurrence of the event.
- Presence of non-treatment-related factors that are known to be associated with the occurrence of the event.

For patient receiving combination therapy, causality will be assessed individually for each protocol-mandated therapy.

5.3.5 PROCEDURE FOR RECORDING ADVERSE EVENTS

Investigator(s) should use correct medical terminology/concepts when recording AEs on the AE eCRF page. Avoid colloquialisms and abbreviations.

Only one AE term should be recorded in the event field on the AE eCRF page.

5.3.5.1 DIAGNOSIS VERSUS SIGNS AND SYMPTOMS

A diagnosis (if known) should be recorded on the AE eCRF page rather than individual signs and symptoms (e.g., record only liver failure or hepatitis rather than jaundice, asterixis and elevated transaminases). However, if a constellation of signs and/or symptoms cannot be medically characterized as a single diagnosis or syndrome at the time of reporting, each individual event should be recorded on the AE eCRF page. If a diagnosis is subsequently established, all previously reported AEs based on signs and symptoms should be nullified and replaced by one AE report based on the single diagnosis, with a starting date that corresponds to the starting date of the first symptom of the eventual diagnosis.

5.3.5.2 ADVERSE EVENTS OCCURRING SECONDARY TO OTHER EVENTS

In general, AEs occurring secondary to other events (e.g., cascade events or clinical sequelae) should be identified by their primary cause, with the exception of severe or serious secondary events. However, medically significant AEs occurring secondary to an initiating event that are separated in time should be recorded as independent events on the AE eCRF page. For example:

- If vomiting results in mild dehydration with no additional treatment in a healthy adult, only vomiting should be reported on the eCRF.
- If vomiting results in severe dehydration, both events should be reported separately on the eCRF.
- If a severe GI hemorrhage leads to renal failure, both events should be reported separately on the eCRF.
- If dizziness leads to a fall and subsequent fracture, all three events should be reported separately on the eCRF.

All AEs should be recorded separately on the AE eCRF page if it is unclear as to whether the events are associated.

5.3.5.3 PERSISTENT OR RECURRENT ADVERSE EVENTS

A persistent AE is one that extends continuously, without resolution, between patient evaluation time points. Such events should only be recorded once on the AE eCRF page. The initial severity of the event should be recorded, and the severity should be updated to reflect the most extreme severity any time the event worsens. If the event becomes serious, the AE eCRF page should be updated to reflect this.

A recurrent AE is one that resolves between patient evaluation time-points and subsequently recurs. Each recurrence of an AE should be recorded separately on the AE eCRF page.

5.3.5.4 ABNORMAL LABORATORY VALUES

Not every laboratory abnormality qualifies as an AE. A laboratory test result should be reported as an AE if it meets any of the following criteria:

- Accompanied by clinical symptoms.
- Results in a change in study treatment (e.g., dosage modification, treatment interruption, or treatment discontinuation).
- Results in a medical intervention (e.g., potassium supplementation for hypokalemia) or a change in concomitant therapy.
- Clinically significant in the investigator's judgment.

It is the investigator's responsibility to review all laboratory findings. Medical and scientific judgment should be exercised in deciding whether an isolated laboratory abnormality should be classified as an AE.

If a clinically significant laboratory abnormality is a sign of a disease or syndrome (e.g., ALP and bilirubin 5 times the upper limit of normal (ULN) associated with cholecystitis), only the diagnosis (i.e., cholecystitis) should be recorded on the AE eCRF page.

If a clinically significant laboratory abnormality is not a sign of a disease or syndrome, the abnormality itself should be recorded on the AE eCRF page, along with a descriptor indicating if the test result is above or below the normal range (e.g., "elevated potassium", as opposed to "abnormal potassium"). If the laboratory abnormality can be characterized by a precise clinical term per standard definitions, the clinical term should be recorded as the AE. For example, a serum potassium level of 7.0 mEq/L should be recorded as "hyperkalemia".

Observations of the same clinically significant laboratory abnormality from visit to visit should not be repeatedly recorded on the AE eCRF page, unless the etiology changes. The initial severity of the event should be recorded, and the severity or seriousness should be updated any time the event worsens.

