Endpoints	
Primary Endpoints - Safety:
 
The safety outcome measures for this study are as follows:
 
• Incidence, nature and severity of adverse events (AEs).• Incidence, nature and severity of serious adverse events (SAEs).• Incidence, nature and severity of adverse events of special interest (AESIs).• Incidence, nature and severity of AEs leading to treatment discontinuation.• Changes from baseline in SBP, DBP, heart rate (HR) and respiratory rate.• Changes from baseline in orthostatic measurements of blood pressure (BP) and HR.• Changes from baseline in ECG parameters (HR, PQ, QRS, QT, RR and QTcF, along with information on T and U waves).• Incidence of clinically significant ECG abnormalities.• Hearing assessment.• Incidence of clinically relevant laboratory abnormalities, based on hematology, coagulation, blood chemistry and urinalysis test results:
○ Hematology: hemoglobin concentration, hematocrit level, erythrocytes and platelet counts, leucocytes differential (absolute) counts (neutrophils, eosinophils, lymphocytes, monocytes and basophils)○ Coagulation: international normalized ratio (INR), activated partial thromboplastin time (aPTT) and prothrombin time (PT)○ Blood chemistry: C-reactive protein (CRP test), aspartate aminotransferase (AST), alanine aminotransferase (ALT), gamma-glutamyl-transferase (GGT), total and conjugated bilirubin, alkaline phosphatase (ALP), albumin, creatine phosphokinase (CPK), creatinine, urea, total protein, total cholesterol, triglycerides, glucose, sodium, chloride, calcium, magnesium, phosphate, potassium○ Urinalysis: protein, blood, glucose, leucocytes, nitrites, pH and crystals.• Incidence of value outside of the normal ranges and of clinically relevant blood chemistry test results for electrolytes:
○ Sodium, chloride, calcium, magnesium, phosphate, potassium 
Secondary Endpoints - Pharmacokinetics:
 
• [REDACTED] plasma concentration will be evaluated at Days 1, 7, and 14 to 18.• Plasma concentrations of [REDACTED] and associated PK parameters: Area under the plasma concentration-time curve ($AUC_{0-\tau}$, $AUC_{0-\text{last}}$, $AUC_{0-\infty}$), minimum plasma concentration prior to administration (C_{trough}), maximum plasma concentration (C_{max}, $C_{\text{max,ss}}$), time of
-----------	--

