3.3 OUTCOME MEASURES

3.3.1 SAFETY OUTCOME MEASURES

The safety outcome measures for this study are as follows:

- Incidence, nature and severity of AEs.
- Incidence, nature and severity of SAEs.
- Incidence, nature and severity of AESIs.
- Incidence, nature and severity of AEs leading to treatment discontinuations.
- Changes from baseline in systolic blood pressure (SBP), diastolic blood pressure (DBP), heart rate (HR) and respiratory rate.
- Changes from baseline in orthostatic measurements of BP and HR.
- Changes from baseline in ECG parameters (HR, PQ, QRS, QT, RR and QTcF, along with information on T and U waves).
- Incidence of clinically significant ECG abnormalities.
- Hearing assessment
- Incidence of clinically relevant laboratory abnormalities, based on hematology, blood chemistry and urinalysis test results:
 - Hematology: hemoglobin, hematocrit, erythrocytes, platelet count, leucocytes differential (absolute) counts (neutrophils, eosinophils, lymphocytes, monocytes, basophils).
 - Blood chemistry: aspartate aminotransferase (AST), alanine aminotransferase (ALT), gamma-glutamyltransferase (GGT), total and conjugated bilirubin, alkaline phosphatase (ALP), albumin, creatine phosphokinase (CPK), creatinine, urea, total protein, total cholesterol, triglycerides, sodium, chloride, calcium, magnesium, phosphate, potassium, glucose.
- Incidence of value outside of the normal ranges of blood chemistry test results for electrolytes:
 - Sodium, chloride, calcium, magnesium, phosphate, potassium
- Urinalysis: protein, blood, glucose, leucocytes, nitrites, pH, and presence of crystals.

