4.6.1.3 VITAL SIGNS

Vital signs will include measurements of temperature, HR, respiratory rate and SBP and DBP, and will be recorded at the time-points specified in the Schedule of Assessments ([Appendix 1](#)). BP and HR measurements should be obtained in a quiet room at a comfortable temperature, with the patient's arm unconstrained by clothing or other material. All measurements will be obtained from the same arm (when possible) and, with the same cuff size, using a well-calibrated automatic instrument with a digital readout, throughout the study. Vital signs should be measured prior to blood draw or at least 10 minutes after the last blood draw.

After the patient has been resting for approximately 5 minutes in a supine position, BP and HR will be recorded. The subject will then be asked to stand, and BP and HR measurements will be repeated after standing 1 and 3 minutes.

A drop in systolic BP of ≥ 20 mm Hg, or in diastolic BP of ≥ 10 mm Hg will be recorded as abnormal and any dizziness, weakness, or visual changes associated with position change will be recorded as an AE.

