5.1.3 ADVERSE EVENTS OF SPECIAL INTEREST (IMMEDIATELY REPORTABLE TO THE SPONSOR)

AESIs are required to be reported by the investigator to the sponsor immediately (i.e., no more than 24 hours after learning of the event; see [Section 5.4.2](#) for reporting instructions). AESIs for this study include the following:

- Electrolyte imbalance: hypokalemia (K⁺ level <3.4 mEq/L), hyperkalemia (>5.0 mEq/L), hyponatremia (Na⁺ level <135 mEq/L), hypochloremia (Cl⁻ level <97 mEq/L)
- Thrombocytopenia is defined as meeting one or both criteria:
 - Platelet count below $150 \times 10^9/L$ (or 150.000 platelets per microliter (mcL))
 - Platelet count drop of $\geq 50\%$ compared to baseline
- Drug-induced liver injury (DILI)
- Dehydration and orthostasis (defined by a fall in systolic blood pressure over 20 mm Hg or a fall in diastolic pressure over 10 mm Hg within 3 minutes of standing).

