5.3.5.5 ABNORMAL VITAL SIGN VALUES

Not every vital sign abnormality qualifies as an AE. A vital sign result should be reported as an AE if it meets any of the following criteria:

- Accompanied by clinical symptoms.
- Results in a change in study treatment (e.g., dosage modification, treatment interruption, or treatment discontinuation).
- Results in a medical intervention or a change in concomitant therapy.
- Clinically significant in the investigator's judgment.

It is the investigator's responsibility to review all vital sign findings. Medical and scientific judgment should be exercised in deciding whether an isolated vital sign abnormality should be classified as an AE.

If a clinically significant vital sign abnormality is a sign of a disease or syndrome (e.g., high BP), only the diagnosis (i.e., hypertension) should be recorded on the AE eCRF page.

Observations of the same clinically significant vital sign abnormality from visit to visit should not be repeatedly recorded on the AE eCRF page, unless the etiology changes. The initial severity of the event should be recorded, and the severity or seriousness should be updated any time the event worsens.

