4.2 Analysis of Safety Variables

Adverse Events

Prior to analysis, all AEs will be recorded and classified on the basis of the Medical Dictionary for Regulatory Activities (MedDRA®) terminology. The number and proportion of patients with at least one AE will be summarized by system organ class (SOC) and by preferred term (PT) within SOC for each treatment group.

Similar tables will be provided to display the number and proportion of patients with at least one treatment-related AE, at least one treatment-related AE that led to study treatment discontinuation, at least one serious AE (SAE), at least one treatment-related SAE, at least one treatment-related SAE that led to study treatment discontinuation, at least one AE of special interest (AESI), and at least one AESI that led to study treatment discontinuation by SOC and by PT within SOC. For the purposes of this study, a treatment-related AE is any AE with a relationship to study drug of 'Related'.

In addition, tables will be constructed to summarize AEs by relationship to study drug and by severity.

A separate AE summary table will be constructed to display the number of patients with at least one AE, the number of patients with at least one treatment-related AE, the number of patients with at least one treatment-related AE that led to study treatment discontinuation, the maximum severity of AE by patient, the highest relationship of AE to treatment, the number of patients experiencing at least one SAE, the number of patients with at least one treatment-related SAE, the number of patients with at least one treatment-related SAE that led to study treatment discontinuation, the maximum severity of SAE by patient, the highest relationship of SAE to treatment, the number of patients with at least one AESI, the number of patients with at least one AESI that led to study treatment discontinuation, and the number of deaths.

All AEs will be provided in data listings as shown in Appendix B. AEs having an end date prior to signing the informed consent for this study will not be displayed in the AE data listings.

Vital Signs

The vital signs parameters of interest include temperature, respiratory rate, and orthostatic blood pressure and orthostatic heart rate.

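### The SAP counts AESIs only from flagged AE records, so the primary AESI incidence can omit some patients who met the protocol's numeric cut-offs

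*Protocol*

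**What the plan says.** **Endpoint.** The Protocol synopsis lists "Incidence, nature and severity of adverse events of special interest (AESIs") among the primary safety endpoints, and section 3.3.1 repeats it.

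**Definition.** Protocol 5.1.3 sets cut-offs with no symptom or significance condition:
- potassium below 3.4 or above 5.0, sodium below 135, chloride below 97 mEq/L (in part: "hyperkalemia (>5.0 mEq/L), hyponatremia");
- platelets below 150 × 10⁹/L, or a fall of at least 50% from baseline;
- dehydration and orthostasis, defined by a fall of more than 20 mm Hg systolic or more than 10 mm Hg diastolic within 3 minutes of standing.

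Drug-induced liver injury is also listed, without a number in that section. Sections 5.1.3 and 5.4 require AESIs to reach the sponsor within 24 hours; section 5.4.2 routes them on the SAE Reporting Form.

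**AE recording.** Section 5.3.5.4 says: "Not every laboratory abnormality qualifies as an AE. A laboratory test result should be reported as an AE if it meets any" of four conditions: symptoms, a change in study treatment, a medical intervention or change in concomitant therapy, or clinical significance in the investigator's judgement. Section 5.3.5.5 has the same structure ("Not every vital sign abnormality qualifies as an AE"). Under section 4.6.1.3, an orthostatic fall of at least 20/10 mm Hg "will be recorded as abnormal and any dizziness, weakness, or visual changes associated with position change will be recorded as an AE". Section 5.3.5.2 keeps mild, untreated dehydration after vomiting off the eCRF.

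**Analysis.** SAP 4.2 tabulates patients with "at least one AE of special interest (AESI") by system organ class and preferred term (Tables 4, 11 and 12). The AESI indicator is a column of the adverse events listing (Data Listing 3).

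**The concern.** The endpoint is defined on measured values, but the count is taken from AE entries. Between the two stands a recording rule that does not name the AESI cut-offs. Nothing says which rule prevails when a value meets 5.1.3 but none of the four conditions in 5.3.5.4 or 5.3.5.5. A site could reason that a value which is not an AE cannot be an AE of special interest, or could send the SAE Reporting Form without opening an AE page.

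The tabulated incidence would then depend partly on investigator recording practice. The exposed items include electrolyte changes expected from a loop diuretic. In arms of 3 to 6 patients, one omitted patient is a large share: 1/6 = 17 percentage points, 1/3 = 33.

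**Working it through.** **Step 1. Trace each definition to the AE page and to an SAP table.**

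| AESI in 5.1.3 | Route to the AE page | SAP table using the 5.1.3 cut-off |
|---|---|---|
| Low potassium | 5.2.1.1 calls for supplements, an intervention under 5.3.5.4: largely captured | None; Table 31 uses the laboratory range |
| High potassium, low sodium, low chloride | Only through symptoms, action or judgement: exposed | None; Table 31 as above |
| Platelets | The same definition is among the individual discontinuation criteria in 3.1.2, and discontinuation is a treatment change: captured if confirmed and acted on, otherwise exposed | None; summary statistics, clinical-significance shift table and a plot only |
| Orthostatic fall | Same route through 3.1.2; 4.6.1.3 names only the symptoms as an AE: exposed if not confirmed or not leading to discontinuation | None; standing readings are listed but not tabulated, and Table 16 is supine only |
| Mild dehydration after vomiting | Kept off the eCRF by 5.3.5.2: exposed | None |

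Table 31 counts by visit, so it also gives no number of patients abnormal at any time after baseline. The orthostatic limits differ as well: strictly above 20/10 mm Hg in 5.1.3, at or above 20/10 in 4.6.1.3. A fall of exactly 20 systolic (with a diastolic fall of no more than 10) is abnormal under one and not an AESI under the other.

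**Step 2. The plan's own figure.** The one design figure that can be recomputed is the sample size: 16/(1 − 0.20) = 20, as stated. It has no bearing on AESIs. The documents give no expected AESI rate, so there is nothing to reproduce on this point.

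**Step 3. Illustration.** Inputs:
- p = 0.149, the hypochloremia rate in Protocol 5.2.1.1. Its cut-off is not given; I assume that it applies at <97 mEq/L.
- n = 12 active patients (6 per dose level, Protocol 6.1), or 9 (6 plus the synopsis minimum of 3 at the highest dose), or 6 in one dose group.
- q = probability that a patient who crosses is entered as a flagged AE. This is unknown, so I show 0 to 1.
- Patients independent, with the same rate at both doses.

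Formulas:
- Expected to cross = n·p
- Expected in the AESI table = n·p·q
- P(at least one crosses) = 1 − (1 − p)ⁿ
- P(table shows none, given at least one crosses) = [(1 − pq)ⁿ − (1 − p)ⁿ] / [1 − (1 − p)ⁿ]

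For n = 12: 12 × 0.149 = 1.79 expected to cross, and 1 − 0.851¹² = 0.856.

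| q | Expected in table (n = 12) | P(none shown, given at least one crossed) |
|---|---|---|
| 0 | 0 | 100% |
| 0.25 | 0.45 | 57% |
| 0.50 | 0.89 | 29% |
| 0.75 | 1.34 | 11% |
| 1 | 1.79 | 0% |

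At q = 0.5 the last column is (0.395 − 0.144)/0.856 = 0.29.

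For n = 9: 1.34 expected to cross, 77% chance of at least one, and 0.67 counted at q = 0.5. For n = 6: 0.89 expected, 62%, and 0.45 counted; the table shows none in 40% of cases where at least one patient crossed.

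A count taken directly from the laboratory data corresponds to q = 1.

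**The case against.** The strongest reply is that a site following the whole protocol will report these values. Sections 5.3.5.4 and 5.3.5.5 prohibit nothing: they leave isolated abnormalities to judgement, while 5.1.3 and 5.4 make AESI reporting mandatory. Section 5.1.1 also allows an abnormal laboratory finding to be an AE. This stands to the extent that the defect is an unresolved conflict. A reader might infer that sites are told not to record threshold-only values; the text does not say that.

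Three other stronger readings are also unsupported.
- **All laboratory and blood-pressure AESIs are lost.** They are not. Hypokalemia reaches the AE page through supplementation, and confirmed platelet or orthostatic findings through discontinuation.
- **The DSMB and the sponsor see the same undercount.** Section 3.1.3 gives the DSMB the safety laboratory data, with specific attention to electrolytes, and vital signs including orthostatic changes. The 24-hour report is not made conditional on the 5.3.5.4 criteria, and the sponsor reviews blinded safety data throughout.
- **The count will be far too low.** This needs q near 0 and a literature rate whose cut-off is not stated.

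It is also fair that the values are not hidden. Data Listings 7 and 9 give every chemistry and hematology result with range flags, Listing 4 gives supine and standing readings, and Tables 30 and 31 report electrolytes outside the normal range. With about 20 patients a reader could count crossings by hand. None of this, however, makes the tabulated AESI incidence match its definition, and that incidence is the endpoint.

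**Conclusion.** The point holds in a limited form. The AESI definition, the AE-recording rules and the SAP's source for the count are not aligned, so the summarised AESI incidence can leave out patients who met 5.1.3. The exposed cases are mainly asymptomatic, untreated hyponatremia, hypochloremia and hyperkalemia; mild dehydration after vomiting; and platelet or orthostatic findings that are not confirmed or do not lead to discontinuation. The gap lies in the summary tables, not in data collection or DSMB oversight.

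The size cannot be fixed from the documents. For hypochloremia alone among 12 active patients, the expected shortfall is 1.79 − 0.89 = about 0.9 patients at 50% recording. It ranges from 0 at full recording to 1.79 at none. These figures rest on applying 14.9% at <97 mEq/L, on independence, and on an assumed q. The misalignment itself rests on none of them. The plan should be changed, because the remedy uses data already collected and concerns a primary endpoint.

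**What to change.** **SAP.** Add one table giving, by treatment, the number and proportion of patients meeting each 5.1.3 cut-off at any post-baseline visit. Derive it from the stored laboratory and blood-pressure data, and include the fall of at least 50% in platelets and the standing-minus-supine fall within 3 minutes. Show baseline status, because the platelet exclusion (criterion 3) applies only below 100,000 and a patient can therefore enter already under the AESI limit. Put the investigator-recorded AESI count in the adjacent column.

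**Protocol.** State whether every value meeting a 5.1.3 definition is entered on the AE page, and whether an AESI sent on the SAE Reporting Form must also appear there. Reconcile sections 3.1.2, 4.6.1.3, 5.1.3, 5.3.5.2, 5.3.5.4, 5.3.5.5 and 5.4.2 on this, including the two orthostatic limits. Which limit applies is for the sponsor to settle; the SAP table should follow the reconciled text.

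**Cost.** One programmed table with no new data collection, and short cross-references in the protocol. The AESI count will probably look less favourable. If the sponsor decides that every crossing is to be entered, sites will file some additional AE entries and reports.
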